12. SUPPORTING DOCUMENTS

Your Initial Application must include a **completed Initial Application Part 1 (On-Line Document)**, the information required in items 1-11 above, and all relevant supporting documents including: consent forms, letters sent to recruit participants, questionnaires completed by participants, and any other material that will be presented, viewed or read to human subject participants.

The consent forms in your approved IRBNet PACKAGE must be used. When creating or editing your consent form, please provide the most recent IRBNet package number at the bottom, right corner of the consent form. This ensures you are using the most "up-to-date" version of the form.

To find your IRBNet package number, go to the MY PROJECTS tab and click on the title of your project. In the PROJECT OVERVIEW page, your IRBNet package number will be listed at the top, next to your project title.

Statistical Analysis Plan

Title of Project: A Chatbot Intervention for Reducing HPV Vaccine Hesitancy

NCT #: NCT05959564

January 14, 2023

We will conduct Analyses of Covariance (ANCOVAs) and multiple regressions to examine the group differences. The primary dependent variables will consist of parents' attitudes and intentions toward vaccinating their children against HPV (both are continuous variables). Secondary dependent variables will consist of chatbot ratings. In ANCOVAs, the key independent variable will be chatbot (personalized, non-personalized, no chatbot control). Covariates will include key demographic variables such as age, gender, and education. In regression analyses, a block structure will be used where the first block will consist of the control variables (i.e., covariates) and the second block will contain the key predictor variables—dummy-coded chatbot variables. We will report standard descriptive statistics and correlation matrices for all key variables.

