Study Protocol

Title of Project: A Chatbot Intervention for Reducing HPV Vaccine Hesitancy
NCT #: NCT05959564
November 16, 2022

INITIAL APPLICATION PART 2

1. Abstract:

The goal of this project is to test the efficacy of a chatbot intervention for reducing HPV vaccine hesitancy among African American parents. This project has two phases. In phase I, in-depth interviews will be conducted with African American parents to evaluate the feasibility and acceptability of the chatbot intervention. In phase II, an online experiment will be conducted to test the effectiveness of the chatbot intervention with African American parents. Results of this project will inform future communication interventions for reducing vaccine hesitancy among African American parents.

2. Subject Selection:

- a. **Recruitment:** In phase I, we will recruit participants from local pediatric offices. We will recruit by distributing flyers in the offices. We will obtain permission from the practices to recruit at their offices. A copy of the flyer is attached to this application (we will submit an addendum if additional changes need to be made to the flyer before distribution). In phase II, participants will be recruited from online survey panels (e.g., Prolific, YouGov, Lucid, etc.). Eligible participants will be invited via email to participate in the study. There will also be screening questions at the beginning of the survey to screen participants to ensure they meet the eligible criteria.
- b. **Eligibility Criteria:** Participants must be 18 years or older, self-identify as African American, are custodial parents or caretakers of a child under the age of 18.
- c. **Rationale:** The burden of HPV-associated diseases (e.g., cervical cancer) is disproportionately higher among African Americans compared to other racial groups. Understanding effective methods of communicating to African American parents about the importance of HPV vaccination is therefore critical.
- d. **Enrollment Numbers:** For phase I, we aim to recruit up to 30 participants. For phase II, we aim to recruit up to 600 participants.
- e. **Rationale for Enrollment Numbers:** The enrollment numbers ensure we have adequate statistical power to detect small effects of the intervention.

3. Procedures:

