For phase I, we will conduct in-depth interviews with up to 30 African American parents recruited from local pediatric offices. To facilitate participation, the interviews will be conducted online via Zoom. During the interviews, participants will be asked to interact with a chatbot designed to answer questions about HPV vaccines. Their opinions about the chatbot and suggestions for improvement will be solicited. Each interview session will last approximately 45 minutes. Only anonymized transcription (using Zoom's transcript function) of the interview will

be saved for later analysis. Interviews will not be audio- or video-taped. Each participant will receive a \$50 store gift card. The cash incentive is needed to encourage participation in the study.

In phase II, participants will complete an online survey. In the survey, participants will first answer questions related to their attitudes toward childhood vaccines. Then they will be directed to interact with a chatbot designed to deliver personalized HPV vaccine messages (tailed to the participant's personality) or a similar chatbot with non-personalized messages. There will also be a control condition where participants receive no HPV vaccine messages. After interacting with the chatbot, participants will answer questions related to their attitudes toward HPV vaccination, intentions to vaccinate their children, as well as other message response measures. Those in the control will answer the same questions without interacting with a chatbot. The survey will take approximately 10 minutes to complete. Participants who complete the survey will be compensated with a small amount of cash paid through the online survey platform (\$1-\$2).

4. Risks:

There are no known risks associated with this research. Participants may opt to exit the interview or survey if they are not comfortable answering any of the questions.

5. Benefits:

There are no direct benefits to participants. This research will result in an improved understanding of the design of effective educational materials about HPV vaccination.

6. Confidentiality:

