The title of the IRB application (Chatbot and Vaccine Acceptance) is different from the title on the consent forms (HPV Vaccine Messaging Study). We want to keep the title on the consent forms general because some of the participants will not interact with a chatbot.

8. Conflict of Interest:

There is no conflict of interest.

9. HIPAA Compliance:

N/A

10. Research Outside of the United States:

N/A

11. Research Involving Prisoners:

N/A

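### Does the SAP need to say which arms supply the chatbot ratings, given that one arm has no chatbot?

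*SAP*

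**What the plan says.** The SAP is a single paragraph. Its primary outcomes are attitudes and intentions toward HPV vaccination. On the rest it says: "Secondary dependent variables will consist of chatbot ratings". It gives one factor for the ANCOVAs: "the key independent variable will be chatbot (personalized, non-personalized, no chatbot control". The regressions use dummy variables for the same factor. No two-level version is given for ratings. On descriptive output it says: "We will report standard descriptive statistics and correlation matrices for all key variables".

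Protocol section 3 (Procedures) never mentions chatbot ratings by name. After attitudes and intentions it adds "as well as other message response measures", and then says of the control arm: "Those in the control will answer the same questions without interacting with a chatbot". Section 7 (Consent Process) explains the neutral title on the consent forms by noting that "some of the participants will not interact with a chatbot". Section 2d sets phase II at up to 600 participants, with no allocation ratio. Section 2e says: "The enrollment numbers ensure we have adequate statistical power to detect small effects of the intervention".

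**The concern.** A person who has used no chatbot cannot rate one, yet the only factor in the SAP includes such people. Taken literally, the plan pairs its secondary outcome with a model that has an empty cell. The protocol's remark that controls get the same questions points the other way, and could be read as putting rating items to people who saw nothing.

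Two consequences seem possible.

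- **If controls give no ratings.** A single correlation matrix with listwise deletion would drop every control, even from the attitude-intention correlation. Pairwise deletion would keep them but mix samples within one table. The two choices would report different figures for the primary variables.
- **If controls do give ratings.** A significant three-group F would not by itself show that the two chatbots are rated differently.

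It also seems that a ratings comparison resting on two arms loses the power for small effects that the protocol claims for the whole sample.

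**Working it through.** The plan states no figure on this point, so there is none to reproduce. The inputs are 600 participants (the ceiling in protocol section 2d) and these assumptions, which the documents do not give: equal allocation (200 per arm), two-sided alpha 0.05, three covariate degrees of freedom (age, gender and education, one each), and no control ratings.

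**1. The group test on ratings.** Write the model as an intercept plus dummies D1 (personalized) and D2 (non-personalized). On all 600 rows the design has rank 3. On the 400 chatbot rows D1 + D2 = 1, which duplicates the intercept, so the rank is 2. One group contrast is left: personalized minus non-personalized. That is the only comparison of ratings that makes sense. The test therefore loses nothing it should contain.

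**2. Rows lost under listwise deletion.** 600 × 1/3 = 200 controls lost and 400 kept. For control shares from 20% to 50%, the loss runs from 120 to 300 and the number kept from 480 to 300.

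**3. Effect on the correlation estimate.** Take unit variances and a within-arm correlation of 0.5, with both chatbots shifting attitudes and intentions by d SD. Pooling the arms adds d² × (1/3) × (2/3) to the covariance and to each variance.

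- d = 0.3: 0.09 × 2/9 = 0.020; all-arm r = 0.520/1.020 = 0.510.
- d = 0.5: 0.25 × 2/9 = 0.0556; all-arm r = 0.5556/1.0556 = 0.526.
- In the chatbot arms alone, r stays at 0.500.

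A simulation of 3,000 datasets agrees: 0.510 and 0.526 in all arms, against 0.499 and 0.500 in the chatbot arms.

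**4. Effect on precision.** On Fisher's z scale the standard error is 1/√(N − 3): 1/√597 = 0.0409 and 1/√397 = 0.0502, a ratio of 1.23. For r = 0.5, z = 0.549:

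| N | z ± 1.96 SE | 95% interval for r |
|---|---|---|
| 600 | 0.549 ± 0.080 | 0.437 to 0.558 |
| 400 | 0.549 ± 0.098 | 0.423 to 0.570 |

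**5. Is the power limit caused by this gap?** Compare the same contrast, personalized against non-personalized, on ratings (two arms, residual df 400 − 2 − 3 = 395) and on a primary outcome (error pooled over three arms, residual df 600 − 3 − 3 = 594). The noncentrality is 200 × d²/2 in both cases.

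| True difference (SD) | Ratings | Primary outcome |
|---|---|---|
| 0.1 | 0.169 | 0.170 |
| 0.2 | 0.514 | 0.515 |
| 0.3 | 0.849 | 0.850 |

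The figures differ by 0.001. The limit comes from having 200 per arm. Naming the arms that supply ratings would not alter it, and section 2e makes no claim about ratings.

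**6. The text on correlations.** The listwise worry needs two things that the SAP does not say: that ratings count among the key variables, and that everything goes into one matrix. The SAP applies the word key to the independent variable, the demographic variables and the predictors, but not to ratings. It speaks of matrices in the plural, which fits one for the full sample and another for the chatbot arms.

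**The case for a change.** The best case for a change is that a plan should fix in advance who contributes to each named outcome, and here the only secondary outcome lacks that. The protocol's wording on the control arm does not settle the matter and, read literally, points the wrong way. A clarifying sentence would be cheap, and if controls really are shown rating items it would be better to learn so before the analysis.

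The silence is real, and that much stands. It does not carry further.

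- **The likelier reading is clear.** The term chatbot ratings presupposes a chatbot, and section 7 of the protocol shows the investigators had in mind that some participants would not meet one.
- **The questionnaire would settle it.** Protocol section 12 requires participant questionnaires in the application package. They are not among the documents reviewed, so what looks open here may be fixed there.
- **The less likely reading inflates no error rate.** If controls did answer rating items, the three-group F would still be a valid test of its own hypothesis. The analyst would need the contrast between the two chatbots, which the dummy-coded regression can supply.
- **A firm edit could be wrong.** Writing into the protocol that controls do not answer the rating items would assert a fact that these documents do not establish.

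**Conclusion.** No change to the plan follows. The SAP leaves out a detail that analysts would fill in the obvious way: compare ratings between the two chatbot arms, and show the number of participants behind any correlation that uses ratings.

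Under 600 participants, equal allocation and no control ratings, the worst handling of the correlation tables moves an attitude-intention correlation by about 0.01 (0.51 against 0.50) for chatbot effects of 0.3 SD, or about 0.03 for effects of 0.5 SD, and widens its interval on Fisher's z scale by about 23%. The SAP ties no hypothesis to those tables and promises no intervals for them, so no conclusion of the trial would turn on the difference.

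The group tests on attitudes and intentions use all three arms and are unaffected. The modest power for a contrast between the two chatbots is a feature of the arm sizes and is practically the same for the primary outcomes, so it adds no weight to this point. The size of the effect on the tables depends on the assumed allocation and achieved sample; the conclusion about the group test on ratings does not.

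### Vaccine attitudes are measured before exposure in phase II, but the SAP's open, demographics-only covariate list does not commit to adjusting for them

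*SAP*

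**What the plan says.** The Protocol, section 3 (Procedures), sets the order of events in phase II. The attitude questions come at the start: "In the survey, participants will first answer questions related to their attitudes toward childhood vaccines". Exposure follows: "Then they will be directed to interact with a chatbot designed to deliver personalized HPV vaccine messages", or a non-personalized version, or no messages in the control condition. The outcomes come last: "participants will answer questions related to their attitudes toward HPV vaccination, intentions to vaccinate their children". The control arm is treated alike in this respect: "Those in the control will answer the same questions without interacting with a chatbot".

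The SAP is a single paragraph. It names two continuous primary outcomes, HPV vaccination attitudes and intentions, compared across three conditions. On adjustment it says only: "Covariates will include key demographic variables such as age, gender, and education". The block regressions carry the same set forward as their first block.

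Section 2e of the Protocol justifies the phase II enrolment of up to 600 with the statement "The enrollment numbers ensure we have adequate statistical power to detect small effects of the intervention". It gives no alpha, power, effect size, standard deviation or allocation ratio.

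**The concern.** A general attitude to childhood vaccines is a plausible predictor of attitude and intention toward HPV vaccination. It is collected before exposure in all three conditions, so the intervention cannot have affected it and it is safe to adjust for. ANCOVA is already the planned method. Even so, neither document assigns the measure any use.

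Two things are at stake.

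- **Precision.** If the score predicts the outcome beyond the demographics, leaving it out gives wider intervals than the data allow. That matters in a study whose stated purpose is to find small effects.
- **Prespecification.** The SAP says covariates *will include* demographics *such as* three examples. The final set is therefore not fixed, and the score could be added or left out once results are known.

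Bias is not the issue. The Protocol calls phase II an experiment, which implies random assignment without spelling it out. If assignment is random, a demographics-only ANCOVA is valid. Nor is the score a baseline of the outcome, because it concerns childhood vaccines in general. Its correlation may also differ between the two primary outcomes.

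**Working it through.** **The plan's own figure.** The enrolment of 600 cannot be reproduced, because section 2e gives no inputs for it. It can be neither confirmed nor called wrong. What follows is a benchmark.

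**Inputs**

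- From the documents: up to 600 participants (Protocol 2d), three conditions and continuous outcomes (SAP).
- Assumed: all 600 recruited and analysed, 200 per arm, two-sided alpha 0.05, a small effect read as d = 0.2 SD, and three demographics using one degree of freedom each.
- Also assumed: r, the partial correlation of the score with the outcome given the demographics, shown from 0.1 to 0.7. The SD is the one left after demographic adjustment.

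**Formulas**

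1. Adjustment multiplies the standard error of a pairwise difference by √(1 − r²).
2. Power comes from the noncentral t distribution with noncentrality d·√(n/2)/√(1 − r²) = 0.2 × √100/√(1 − r²) = 2/√(1 − r²). Degrees of freedom are 600 − 3 − 3 = 594 without the score and 593 with it.
3. The detectable difference is the d that gives 80% power in the same function.
4. The equivalent sample size is 600/(1 − r²).
5. Type I error, if either model may be reported, is P(|z₁| > 1.96 or |z₂| > 1.96) under the null, where the two test statistics have correlation √(1 − r²).

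**Results**

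| r | √(1 − r²) | Power for d = 0.2 | Detectable difference at 80% power (SD) | Equivalent N | Type I error if the better model is chosen |
|---|---|---|---|---|---|
| score not used | 1 | 51.5% | 0.281 | 600 | 5.0% (one fixed model) |
| 0.1 | 0.995 | 51.9% | 0.279 | 606 | 5.5% |
| 0.2 | 0.980 | 53.1% | 0.275 | 625 | 5.9% |
| 0.3 | 0.954 | 55.3% | 0.268 | 659 | 6.4% |
| 0.5 | 0.866 | 63.5% | 0.243 | 800 | 7.3% |
| 0.7 | 0.714 | 79.8% | 0.200 | 1176 | 8.3% |

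Worked line for r = 0.5: the noncentrality is 2/0.866 = 2.309, which gives 63.5% power, and the equivalent N is 600/0.75 = 800.

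**Chance imbalance.** With 200 per arm, the 95% limit for a chance difference in the score is 1.96 × √(2/200) = 0.196 SD. A difference of that size shifts the estimate that omits the score by r × 0.196 SD: 0.02 at r = 0.1, 0.06 at 0.3, 0.10 at 0.5 and 0.14 at 0.7. This is the same precision loss seen in a single unlucky sample, not a further harm.

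**The case against.** The strongest reply is that choosing demographic covariates is a legitimate efficiency decision and no passage contradicts another. The gain rests wholly on r, about which the documents are silent. The items are about childhood vaccines in general, so r may be modest. The power gain is then small: 0.4 points at r = 0.1, 1.6 at 0.2 and 3.8 at 0.3. That stands. The top row of the range should not be read as an expectation.

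It can also be said that *such as* qualifies the demographics, so that on a natural reading an attitude score is simply not planned. The type I error figures would then describe something nobody intends. This stands in part: nothing in the SAP says two models will be fitted and the better one kept. But *will include* does not close the list either, and no sentence excludes the score. The figures show what the wording permits, not what the sponsor means to do.

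Finally, the questionnaire is not among the documents reviewed. Whether the items form one continuous scale or several subscales, or serve another purpose, is unknown. That is why a scoring rule has to accompany the change.

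None of this argues for leaving the matter undecided. If r is small, including the score costs about one degree of freedom out of 594.

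**Conclusion.** The concern holds. A pre-exposure measure that plausibly predicts both primary outcomes is collected, has no stated analytic role, and is neither in nor out of the covariate set. The planned analysis remains valid if assignment is random, so this is an improvement that should be made rather than a flaw that undermines the trial.

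The omission is certain from the text; its cost is not. Under the stated assumptions, the gain from adjusting is negligible for r up to about 0.2 and modest at 0.3. From about 0.5 it is material: 12 points of power (63.5% − 51.5%), equivalent to 200 more participants (800 − 600). Fixing the covariate list is worthwhile at any r, because it removes the opportunity to choose the model after seeing results. Adjustment would help with differential dropout only to the extent that this score explains the dropout.

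**What to change.** Before outcome data are seen, replace the SAP's covariate sentence with wording such as:

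> Covariates in both primary ANCOVAs and in regression block 1 are the pre-intervention childhood-vaccine attitude score (continuous, scored as defined below), age, gender and education; no other covariate enters a primary model.

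Directly beneath it, define the score: which items, their direction, mean or sum, and how missing items are handled. The sponsor must supply this from the questionnaire. If other demographics are wanted, name them in the same sentence; what matters is that the list is closed. If outcome data have already been seen, say so and label the score-adjusted analysis as added afterwards.

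The cost is one replaced sentence and one scoring definition. The questions are already in the survey, so no new data or participants are needed. The model loses about one degree of freedom if the items form a single scale, or one per subscale otherwise.
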